### **9.2.3. HCP and Patient Awareness Strategies**

Study enrollment is open to all eligible pregnant women; however, a number of strategies will be employed to increase likelihood of enrollment. Registry awareness approaches may include, but are not limited to the following:

- Product label to include registry contact information adhering to FDA's Pregnancy and Lactation Labeling Rule (PLLR)
- List the registry on FDA's listing of pregnancy registry site  
<https://www.fda.gov/ScienceResearch/SpecialTopics/WomensHealthResearch/ucm251314.htm>
- List the registry on various pregnancy focused organizations websites (e.g., ACOG, Society for Maternal Fetal Medicine (SMFM) listing of registries)
- List the registry on Syneos Health's Active Pregnancy Registries web page
- Medical journal advertising and/or direct to physician advertising

- Outreach to treating/reporting HCPs (headache/migraine specialists, neurologists, internists, family practice, obstetrician/gynecologists) and patients including an announcement of the registry in appropriate organization newsletters targeting both healthcare providers and patients (professional societies such as American Headache Society, American College of Obstetricians and Gynecologists (ACOG), patient advocacy groups)
- Scientific presentations and publications

#### **9.2.3.1. Dedicated Reporters**

An active dedicated reporter model will be used to assist with patient identification. This strategy will entail reaching out to migraine/headache providers and obstetrician/gynecologists in a broad variety of settings. A recruitment strategy will target maternal HCPs that are known to treat headache/migraine/cluster headache as well as pregnancy providers. A dedicated reporter is a healthcare professional (prescribing/treating/reporting physician) that agrees to actively enroll all eligible patients who provide consent among their patient population. Dedicated reporters are not considered site investigators. They follow the centralized IRB approval for the overall registry. By committing to actively identify and report all eligible consenting patients in their care, they substantially contribute to the enrollment and number of evaluable (i.e., those for whom pregnancy outcome and congenital anomaly assessment is obtained) women in the analysis. Written assurance is required of all dedicated reporters that they agree to adhere to the set conditions.

Dedicated reports are a subset of total HCP reporters contributing to the registry. They are identified based on their anticipated eligible patient population which might include targeted outreach organizations (e.g. American Headache Society, ACOG), academic medical centers, and others identified as likely prescribers of galcanezumab to women of reproductive age. Migraine may be treated by neurologists, internal medicine, family practice, or ob/gyn physicians. Intelligence on prescribing practices will be utilized where available to assist with identifying potential reporters.

#### **9.2.4. Selection of Comparison Data**

The registry will enroll two comparator groups: unexposed to CGRP migraine controls and non-migraine general population controls. This study will also use external published migraine and population-based comparator data to provide context for the events observed in the galcanezumab cohorts.

##### **9.2.4.1. Internal Comparison Groups**

The registry will attempt to enroll 420 women with migraine not exposed to CGRP antagonists (i.e., not treated with CGRP antagonists but *may* have been treated with other prescribed or over-the-counter migraine therapies) and 420 general population controls (i.e., do not suffer from migraines). While women with migraines untreated with any therapy may be included in the comparison group, the comparison group should not be made up entirely of untreated women. Migraines are associated with some baseline pregnancy risks and comorbidities and limiting to untreated controls may introduce bias among a group of women with less severe disease,

exposure to other migraine treatments or other fundamental population differences with potentially differential pregnancy outcomes.

For the CGRP antagonist-untreated migraine controls, the reporting HCP for the galcanezumab-exposed pregnant women will be asked to identify and enroll a CGRP antagonist-unexposed migraine control patient (but who may have been treated with other prescribed or over-the-counter migraine therapies). This will help to ensure that there is general balance in the overall registry enrollment. Should the reporting physician not be able to identify an eligible CGRP antagonists-unexposed control patient, the internal comparison group could be supplemented with self-referred pregnant women who suffer from migraines. Additionally, the subset of dedicated reporting physicians (see above) can serve as a source of CGRP antagonist-unexposed pregnant migraine patients.

Reporting maternal HCPs, including the group of dedicated reporting physicians (see above) can serve as referral sources of pregnant women with migraine, as well as the general population controls without migraine. For the general population controls without migraine, an additional supplemental approach, if needed, will be to invite enrolling women in either the galcanezumab exposed or GCRP antagonist-unexposed groups to “refer a friend” without migraines to participate. The internally enrolled general population controls without migraine approach will provide a directly comparable background comparison group overcoming the traditional limitations of external comparators.

#### **9.2.4.2. External Comparator Data**

The use of external comparators will be considered as supplemental, exploratory comparison groups to contextualize the findings of the registry. The published final results of the Sumatriptan, Naratriptan, Treximet Pregnancy Registry (Ephross and Sinclair 2014) represent a readily available external non-CGRP antagonist exposed historical pregnant migraine population. However, it is important to note that only major birth defects apparent at birth were captured, as infants were not followed up to one year of age. In addition, while some pregnancy outcomes including spontaneous abortions, fetal death/stillbirths and elective terminations were collected, other outcomes of interest such as pre-eclampsia, hypertension during pregnancy, preterm birth, small for gestational age, and postnatal growth/ development through one year of age were not collected.

Published results from the Metropolitan Atlanta Congenital Birth Defects Program (MACDP) for congenital malformations, as well as published data for other outcomes of interest (e.g. the CDC National Vital Statistics System (NVSS) for the US prevalence of preterm birth (Martin et al. 2015) can serve as a secondary supplemental background comparator with the internally enrolled comparison group as the primary comparator. While the MACDP is considered to be the standard coding criteria for congenital malformation evaluation, there are well known limitations such as geographic representation and patient demographics that are not ideally reflective of the whole US population. External comparators are still useful to allow the assessment of generalizability of this study’s findings and any other future study findings.

Should other newly available or newly identified appropriate supplemental migraine and/or population-based comparison data from the literature and other sources, such as other pregnancy registries or observational studies become available, these will be evaluated as possible additional data to contextualize further the results of this study.

### **9.3. Variables**

#### **9.3.1. Exposure of Interest**

The exposure of interest is treatment with galcanezumab at any time during pregnancy or up to 4 months prior to conception. Any injection of galcanezumab within 4 months prior to the LMP is considered exposed due to its long half-life. Data will be collected regarding dates of treatment and number of doses. The trimester of exposure will also be captured.

CGRP antagonist-unexposed women with migraine will not have been treated with CGRP antagonists at any time during pregnancy or up to 4 months prior to conception, but may have been treated with other prescribed or over-the-counter migraine therapies.

Treatment is not under control of the study but administered solely at the discretion of the pregnant woman's treating HCP and as part of routine clinical care. Only data that are routinely recorded in the course of usual care among women treated with galcanezumab during pregnancy will be collected.

#### **9.3.2. Congenital Malformations, Pregnancy Outcomes, Maternal Pregnancy Complications, Infant Outcomes and Infant Events of Interest**

##### **9.3.2.1. Pregnancy outcome**

Each **pregnancy outcome** will be reported as one of the following:

- Live birth: an infant born alive
- Stillbirth: a fetal death occurring at 20 weeks' gestation or greater, or if gestational age is unknown, a fetus weighing 500 g or more
- Recognized spontaneous abortion (SAB): fetal death or expulsion of products of conception prior to 20 weeks' gestation. Terminology may include missed abortion, incomplete abortion, and inevitable abortion.
- Elective termination: voluntary interruption of pregnancy, including pregnancy termination that occurs electively, to preserve maternal health, or due to abnormalities
- Ectopic pregnancy: implantation of a conception outside of the uterus
- Molar pregnancy: a conception that results in a gestational trophoblastic tumor

Maternal death will be assessed on a case-by-case basis to determine if it is an evaluable or non-evaluable patient.

Pregnancy outcomes may occur in presence or absence of a congenital malformation (see Section 9.3.2.2).

### **9.3.2.2. Congenital Malformations**

The study defines and codes congenital malformations with criteria specified by CDC MACDP (CDC 2007). A major congenital malformation (MCM) is defined as any major structural or chromosomal defect in live-born infants, stillbirths, or fetal losses of any gestational age (including outcomes prior to 20 weeks' gestation or birth weight <500 g). This definition is consistent with, but not restricted to, the CDC MACDP definition. Clusters of conditional abnormalities (i.e., minor congenital malformations as defined by CDC MACDP) and data from aborted fetuses of less than 20 weeks' gestation, when available, will be included to increase sensitivity of monitoring. The MACDP includes conditional defects only if in the presence of a major defect. This study will consider reports of three or more conditional defects as a defect case, to increase case detection sensitivity and to capture instances where a combination of conditional events might constitute a major defect or syndrome.

The study conforms to the CDC MACDP guidelines; it disqualifies as defects those findings that are present in infants born at less than 36 weeks of gestation and which are attributable to prematurity itself (such as patent ductus arteriosus, patent foramen ovale, or inguinal hernias). The CDC MACDP classification does include chromosomal defects. Though these defects are not likely to contribute to a risk for a medication exposure, the study includes these defects to maintain this consistency with the CDC MACDP.

Live-born infants with only transient or infectious conditions or with biochemical abnormalities will be classified as being without reported congenital malformations unless there is a possibility that the condition reflects an unrecognized defect. Detected and reported transient or infectious conditions or biochemical abnormalities in infants without reported MCMs and defects that are excluded by the CDC guidelines will be noted in an appendix in the study reports.

The Registry will systematically collect information on major structural and chromosomal defects that are apparent at birth and noted through infant age one year: congenital malformation(s) and details, if noted, type of congenital malformation(s) if applicable, attribution to drug therapy, and other factors that might have contributed to the outcome.

If a congenital malformation is reported, other data of interest can be collected through targeted follow-up.

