### **9.7.2. Statistical Methods**

Overall and stratum-specific (e.g., timing of exposure to galcanezumab (prior to conception vs. during pregnancy, as well as trimester of exposure), maternal age group) point estimates and 2-sided 95% confidence intervals will be calculated using the exact binomial distribution for prevalence of congenital malformations among evaluable patients, preterm birth and SGA among evaluable patients with live births, preeclampsia and hypertension in pregnancy and infant growth and development through one year for each of the galcanezumab exposed, CGRP antagonist-unexposed migraine and general population, non-migraine groups.

If applicable, frequencies of the events of interest will be presented by pregnancy outcome.

Most structural defects have their origins in the first trimester of pregnancy, the period of organogenesis. In addition to overall prevalence of observed MCM, the analysis of MCMs will be stratified by trimester of earliest exposure to galcanezumab. The prevalence of combined MCMs reported to the study will be calculated as a proportion with the number of observed MCMs as the numerator and the number of live births as the denominator, among women with first trimester exposure. CDC MACDP uses these figures to calculate the prevalence, and in order to compare the observed study prevalence with the background prevalence, it is decided to use the same method. Pregnancy losses occurring at or after 20 weeks' gestation with reported MCMs will be included in the numerator of the estimate of prevalence for MCMs as a conservative approach. This method also allows comparison of outcomes with the CDC MACDP. The reason MACDP uses this method is because a slight overestimate is preferred to a potential underestimate. This is due to not taking into account stillbirths in the denominator (but counting the MCM's recognized in stillbirths in the numerator). However, given the very low prevalence of stillbirths as pregnancy outcomes in the general population, this is only a very small possible overestimate. The prevalence of observed MCMs in exposed cases will be compared with the most recent reported prevalence of the CDC MACDP. Additionally, if a sufficient sample size is attained for each trimester exposure group, it may be possible to compare the prevalence of MCMs among exposures to galcanezumab in the first trimester versus

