those in the second or third trimester combined, in addition to the migraine and general population, non-migraine controls.

Only congenital malformation cases meeting the CDC MACDP criteria for a major defect or with three or more minor malformations (e.g., conditional defects) will be included in the primary analysis. In the absence of a major malformation, one or two minor defects do not constitute a MCM according to the CDC MACDP classification; therefore, they will be listed in the report, but not counted as an MCM case in the primary analysis.

The prevalence of preterm births and SGA will be calculated as proportions, with the number of live births as the denominator. The prevalence of preterm birth and SGA in exposed cases will be compared with that in the two comparison groups, as well as with published data, including the most recent reported data by the CDC NVSS. Because MCMs and also multiple gestation pregnancies are often associated with preterm birth and SGA, these infants will be excluded from analyses of these outcomes and will not be counted in the numerator or denominator when prevalence is determined.

For this study, gestational weeks are estimated from the most reliable EDD as reported by the HCP. If a CEDD is provided by the HCP, it will be used instead. The date of conception will be calculated as the most reliable EDD minus 38 weeks. If the EDD is not available or never estimated, the first day of the LMP may be used to estimate gestational age. The second trimester will be considered to begin at week 14, and the third trimester, at week 28. If there is a discrepancy between gestational age calculated from LMP and reported gestational age, the HCP will be asked to verify the data.

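### The primary MCM numerator counts conditional-only clusters that the protocol says MACDP does not count, yet the resulting prevalence is compared with MACDP's as if the method were the same

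*Protocol*

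**What the plan says.** Protocol section 9.3.2.2 sets the case definition and describes its relation to the benchmark: "This definition is consistent with, but not restricted to, the CDC MACDP definition". It states the benchmark's own rule, "The MACDP includes conditional defects only if in the presence of a major defect", and then departs from it: "This study will consider reports of three or more conditional defects as a defect case". The reason given is sensitivity of case detection.

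Section 9.7.2 carries the wider rule into the main estimate. Cases that meet the MACDP criteria for a major defect "or with three or more minor malformations (e.g., conditional defects) will be included in the primary analysis". For women with first-trimester exposure, prevalence is calculated "with the number of observed MCMs as the numerator and the number of live births as the denominator".

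The same section says that MACDP uses these figures, that the registry has adopted the same approach so that the two prevalences can be compared, and that exposed cases will be compared with MACDP's most recent figure. After describing how losses from 20 weeks are handled, it adds: "This method also allows comparison of outcomes with the CDC MACDP". The only source of overestimation it names is that stillbirths are absent from the denominator, and it calls that effect very small.

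Section 9.2.4.2 makes MACDP a secondary, supplemental comparator behind the internal groups. The limitations it names for MACDP are geography and demographics. Case definition is not among them.

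**The concern.** A prevalence can be set against a benchmark only if the numerators count the same things. By the protocol's own account they do not: an infant with three conditional defects and no major defect is a case in the registry and not a case in MACDP. The text that justifies the comparison deals with the denominator and with late losses, and does not mention the wider numerator. No section plans an MCM prevalence restricted to what MACDP would count.

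Section 9.7.2 also says that one or two minor defects without a major one are not an MCM under the MACDP classification. That suggests three or more would be, which conflicts with section 9.3.2.2.

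At stake is how a raised ratio to MACDP would be read in a safety registry. As written, part or all of such a rise could come from the case definition, and the planned comparison could not show how much.

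**Working it through.** **Side-by-side comparison of the rules**

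| Infant or fetus has | Registry primary analysis (9.7.2) | MACDP, as described in 9.3.2.2 |
|---|---|---|
| Major defect, with or without conditional defects | counted | counted |
| Three or more conditional defects, no major defect | counted | not counted |
| One or two conditional defects, no major defect | listed, not counted | not counted |

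The rules differ only in the second row, so on this point the registry numerator is at least as large as a MACDP-rule numerator. The direction is fixed and needs no assumption.

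**Inputs for the size**
- Live births: section 9.5 gives about 350 to 400. This reproduces: 420 × 0.83 = 348.6 and 420 × 0.95 = 399.
- Background: 2.78%, from section 9.5. No source is given there, so it is used only as an illustrative fixed benchmark.
- Interval: exact binomial, two-sided 95%, from section 9.7.2.
- Extra prevalence e from conditional-only cases: **assumed**, 0.10 to 1.0 percentage points, because the protocol gives no rate.
- Drug effect: none.

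**Weight of one case.** At 400 live births one case adds 1/400 = 0.25 points, and 0.25/2.78 = 9.0% of the benchmark. At 350 it adds 1/350 = 0.286 points, or 10.3%. Expected background cases are 400 × 0.0278 = 11.1 and 350 × 0.0278 = 9.7.

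**Effect on the comparison.** The exact 95% interval lies wholly above 2.78% when the case count x satisfies P(X ≥ x | n, 0.0278) ≤ 0.025.
- n = 400: the smallest such x is 19 (tail probability 0.018; at 18 it is 0.033).
- n = 350: the smallest such x is 17 (tail probability 0.020; at 16 it is 0.038).

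With conditional-only cases included, X is binomial with probability 0.0278 + e. The ratio is (2.78 + e)/2.78.

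| Assumed e (points) | Ratio to 2.78% | Extra expected cases, n = 400 | P(X ≥ 19), n = 400 | P(X ≥ 17), n = 350 |
|---|---|---|---|---|
| 0 (MACDP-countable only) | 1.00 | 0 | 1.8% | 2.0% |
| 0.10 | 2.88/2.78 = 1.04 | 0.4 | 2.5% | 2.7% |
| 0.25 | 3.03/2.78 = 1.09 | 1.0 | 3.8% | 4.0% |
| 0.50 | 3.28/2.78 = 1.18 | 2.0 | 7.1% | 7.2% |
| 1.0 | 3.78/2.78 = 1.36 | 4.0 | 18.5% | 17.7% |

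The estimate in section 9.7.2 is restricted to first-trimester exposure, and the protocol does not project how many live births that will include. The 350 to 400 figure stands in for it. If the true denominator is smaller, each case weighs more.

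**The case against.** The best defence is that the sameness claimed in section 9.7.2 concerns arithmetic, not case definition. It follows the description of MCMs over live births and the treatment of late losses. On case definition, section 9.3.2.2 openly says the study goes beyond MACDP and explains why. This stands in part: the wider definition is disclosed and is reasonable for signal detection. It does not rescue the comparison, because the prevalence to be compared includes the extra cases and the protocol never says so where it makes the comparison.

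Second, MACDP is supplementary, the internal comparisons apply one rule to all groups, and any bias runs towards a false signal rather than a missed one. All of that stands and limits the importance of the point. The preference for slight overestimation in section 9.7.2 is argued only for the stillbirth denominator.

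Third, the analysis plan, not available here, may add a restricted count. It may, but the protocol itself fixes the numerator, the comparison and the justification, and those statements would still conflict.

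Two stronger readings are tempting, and the documents do not support them.
- A reader might infer that the study-size statement is undermined. The source of 2.78% is not given, so it cannot be taken as MACDP's figure. The stated 80% power reproduces to within a point: an exact test of 420 pregnancies against a fixed 2.78%, two-sided 5% assumed, rejects at 20 or more cases with 79.1% power at twofold risk. The fix changes neither 420 nor 2.78%.
- A reader might infer from "The Registry will systematically collect information on major structural and chromosomal defects" that minor defects are captured haphazardly and perhaps differently by exposure. That sentence goes on to malformation details and type. Section 8 includes minor malformations in the primary objective, section 9.4.1.3 collects malformations at 4 and 12 months, section 9.4.4 has the provider describe any malformation, and section 9.7.2 lists even one or two minor defects.

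The inclusion of chromosomal defects is no part of this point either: section 9.3.2.2 includes them in order to match MACDP.

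**Conclusion.** The point holds for the MACDP comparison only. The registry numerator is wider than MACDP's by the protocol's own description, the effect can only be upward, and no section corrects or flags it. The size is unknown. Under the assumptions above (no drug effect, 400 live births, a fixed 2.78% benchmark, 0.1 to 1.0 extra points), the ratio would be 1.04 to 1.36 instead of 1.00. The chance of an apparent excess would be 2.5% to 18.5% instead of 1.8%. If conditional-only clusters are rare, the lower end applies and the effect is slight. The calculation does not show that a false signal is likely. The change is worth making because the error has a known direction and is cheap to remove. It does not bear on the internal three-group comparisons.

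**What to change.** 1. Keep the wider definition, with clusters of three or more conditional defects, for the internal comparisons and signal detection.
2. For every comparison with MACDP, use an MCM count limited to MACDP-countable cases: a major defect present, with losses counted as section 9.7.2 already states.
3. Reword section 9.7.2 so that the claim of a shared method covers only what is shared, and say that the wider count is not comparable with MACDP.
4. Reconcile the statement in section 9.7.2 about one or two minor defects under the MACDP classification with the rule given in section 9.3.2.2.

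The cost is one derived flag, one extra table row and two text edits. A teratologist or geneticist already classifies every reported malformation by the MACDP system (section 9.4.4), so no new data are needed and the study size does not change.

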### **9.4.4. Operational Outcome and Event Definition and Identification Process**

All pregnancy outcome and maternal/infant events of interest variables will be provided by the treating or obstetric HCP and the infant's pediatrician. In case no data on the pregnancy outcome can be obtained from the HCP, the pregnant woman will be asked to provide information on the pregnancy outcome. The HCP will be asked to describe any congenital malformations observed in the infant or fetus at birth and will also be asked to report the gestational age and birthweight, as described in the medical records. These last two variables will be used to calculate preterm birth (gestational age <37 weeks at birth) and SGA (birth weight  $\leq$ 10th percentile for gender and gestational age) in live births. A teratologist/geneticist will review all reported congenital malformations and classify them using the CDC's MACDP system as specified in 9.3.2.

This review includes identification of specific aspects of the case for further inquiry from the reporter(s), clarification and classification of the defect(s) reported (in accordance with the classification conventions of the MACDP (CDC, 1998) and a classification system, developed by Scheuerle (Scheuerle and Tilson, 2002) to increase the ability to generate potential signals. In addition, the review includes definition of the potential relevance of timing of exposure to the event(s) reported –'temporality assessment'.

The congenital malformation evaluator assessment includes the following:

- The evaluator may assess a report as "pending further information" if more information is needed to determine the etiology of the defect and/or the temporality. However, if no further information is received despite repeated attempts, the evaluator makes an assessment based upon available information.

The assessments of temporality with the Registry drug exposure are classified as one of the following:

- Pending
- The development of this defect and the timing of the exposure to drug cannot rule out a possible association
- No temporal association
- Unable to assess
- Defect with known cause, temporality may be irrelevant
- Pathogenesis of this defect has yet to be defined specifically enough to assess temporality
- Not a defect

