## 9.5. Study Size

The study aims to enroll a minimum of 420 prospectively enrolled evaluable pregnant women with galcanezumab exposure. Approximately 420 galcanezumab exposed pregnancies are needed to have 80% power to detect a 2.0 fold difference in the baseline risk of major malformations (2.78%) relative to women in the general population.

Assuming 10% loss to follow-up, it is anticipated that approximately 470 patients need to be enrolled. Research indicates that approximately 83% to 95% of pregnancies enrolled in pregnancy exposure registries result in a live birth (Covington et al. 2010), resulting in a lower estimate of approximately 350 and an upper estimate of 400 live births.

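### Chromosomal defects are counted as MCM cases only to match MACDP; a co-reported MCM estimate without them would be a cheap improvement for the internal cohort comparisons

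*Protocol*

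**What the plan says.** Section 9.3.2.2 defines an MCM as a major structural or chromosomal defect. On the chromosomal ones it says: "Though these defects are not likely to contribute to a risk for a medication exposure, the study includes these defects to maintain this consistency" with MACDP. No other reason for including them is given.

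Section 9.7.2 sets the numerator for the primary analysis: "Only congenital malformation cases meeting the CDC MACDP criteria for a major defect or with three or more minor malformations". It describes no MCM estimate without chromosomal defects. It compares MCM prevalence with MACDP and, sample size permitting, with the migraine and non-migraine cohorts.

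Section 9.2.4.2 ranks the comparators: MACDP is secondary and supplemental, and the internally enrolled group is primary. Under section 8, relative occurrence against the two cohorts is a secondary objective, to be estimated where statistically feasible.

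Section 9.5 states that about 420 exposed pregnancies give "80% power to detect a 2.0 fold difference in the baseline risk of major malformations (2.78%) relative to women in the general population".

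Under section 9.4.4 a teratologist/geneticist reviews and classifies every reported malformation. One temporality category is "Defect with known cause, temporality may be irrelevant".

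**The concern.** The protocol counts as cases a group of events that it considers unlikely to be related to medication, and justifies this only by comparability with an outside surveillance programme. In the contrast with MACDP that is sound, because both sides count the same things. In the contrast with the two enrolled cohorts, MACDP comparability plays no part: one evaluator process classifies all reported malformations, so any case definition can be applied alike to every cohort.

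Events that exposure does not change add equally to both sides of a risk ratio and pull it toward 1. In a safety registry that direction is the unhelpful one, since a real rise in the other malformations would look smaller than it is.

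**Working it through.** **Inputs.** From section 9.5: n = 420 exposed, baseline p0 = 2.78%, ratio 2.0, power 80%. From section 9.2.4.1: 420 women per comparison cohort. Section 9.5 gives no test, alpha or sidedness; alpha 0.05 is assumed. The chromosomal share f of the 2.78% is not in the protocol; 5% to 20% is assumed.

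**1. The plan's own figure.** The exposed cohort is tested against a fixed 2.78%, with p1 = 2 x 2.78% = 5.56%.
- Normal approximation, one-sided 0.05, variance under p1: n = (1.645 + 0.842)² x 0.0556 x 0.9444 / 0.0278² = 420.
- Exact binomial, upper tail 0.025: critical count 20, power 79.1% at n = 420.

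The stated figure reproduces for a doubling of all MCMs.

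**2. Attenuation.** If only non-chromosomal defects double, total risk is 2 x p0(1 - f) + p0 x f = p0(2 - f), so the ratio is 2 - f. For the total to double, the non-chromosomal risk must rise (2 - f)/(1 - f)-fold.

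| Assumed f | Ratio seen in all MCMs | Non-chromosomal rise that doubles the total |
|---|---|---|
| 5% | 1.95 | 2.05 |
| 10% | 1.90 | 2.11 |
| 15% | 1.85 | 2.18 |
| 20% | 1.80 | 2.25 |

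In counts: 420 x 0.0278 = 11.7 cases are expected in an unexposed cohort, of which 5% to 20% is 0.6 to 2.3 cases.

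**3. Internal comparison, 420 versus 420.** Pooled two-sided z-test at 0.05, power by exact enumeration. If all MCMs double, power is 52.3%. If only non-chromosomal MCMs double:

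| Assumed f | Counting all MCMs | Excluding chromosomal (baseline p0(1 - f)) |
|---|---|---|
| 5% | 48.8% | 50.2% |
| 10% | 45.2% | 48.0% |
| 15% | 41.7% | 45.8% |
| 20% | 38.2% | 43.6% |

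The restricted analysis does better at each assumed f despite fewer events, by about 1 to 5 points, and it estimates the ratio of 2.0 without attenuation.

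**4. External comparison under the same alternative.** Power at n = 420 for f = 5%, 10%, 15%, 20%:
- Exact test, all MCMs: 75.4%, 71.4%, 66.9%, 62.1%.
- One-sided normal formula from step 1, all MCMs: 77.2%, 74.1%, 70.8%, 67.2%.
- Exact test, chromosomal defects removed from both numerator and baseline: 78.6%, 78.1%, 77.5%, 68.8%.

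These powers are for a doubling confined to non-chromosomal defects, which is not the effect section 9.5 names.

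**The case against.** A reader might infer from step 4 that the 80% in section 9.5 is overstated. The protocol does not support that. Section 9.5 claims power for a doubling of the risk of major malformations as a whole. Section 9.3.2.2 defines that whole to include chromosomal defects, and the figure reproduces. Lower power against a different alternative does not make the stated power wrong. The drop also depends on the formula: a two-sided normal approximation with separate null and alternative variances gives 86.0% for a full doubling and still 83.3% and 80.3% at f = 5% and 10%.

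Other points on the plan's side also stand. The inclusion is deliberate, disclosed and right for the MACDP contrast; dropping chromosomal defects from the registry numerator alone would bias that comparison. The size of f is assumed. Section 9.2.2 excludes ongoing pregnancies with an abnormality found on a prenatal test, which should lower f among enrolled cases. The primary objective is descriptive, and the internal comparisons are secondary and conditional on feasibility. The SAP, which is not shown, may already contain a restricted analysis, and nothing in the protocol prevents one.

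What this leaves is narrow. The protocol itself fixes the case count and the single reason for it, and that reason does not apply to the comparator it calls primary.

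**Conclusion.** The point holds as a cheap improvement, not as an error. In the internal comparisons, a doubling of non-chromosomal malformations would appear as 2 - f: 1.95 to 1.80 for an assumed f of 5% to 20%, and closer to 2 if prenatal exclusions make f smaller. The direction is certain for any f above zero, provided exposure leaves chromosomal defects unchanged, as the protocol expects. The size cannot be derived from the protocol.

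It would be too much to say that this dilution explains the weakness of the internal contrast. With 420 per cohort, power is about 52% even if all MCMs double, and removing chromosomal defects adds only about 1 to 5 points under the narrower alternative. Nor does exclusion bring the external contrast to 80% at n = 420. The main gain is a less attenuated ratio. All these powers take 420 analysed women per cohort at face value.

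**What to change.** - **Section 9.7.2:** keep the MACDP-consistent total MCM estimate as it stands. Prespecify a co-reported MCM estimate excluding chromosomal defects for the comparisons with the migraine and non-migraine cohorts. Apply the exclusion identically in all three cohorts, using the evaluator's existing classification of the defect. The defect class is safer than the temporality category, because temporality is judged against exposure to the registry drug and a known cause need not be chromosomal.
- **Section 9.5:** leave 420 and 80% unchanged. Add that the 2.0-fold effect refers to all MCMs, including chromosomal defects.
- If the SAP already contains the restricted estimate, a cross-reference is enough.

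Cost: a few sentences and one extra table, with no new data and no additional participants. The downsides are two MCM figures to explain and slightly fewer events in the restricted analysis.
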